#### *Handling of missing damage scores*

##### *Step 1. Handling of assessments with partially missing data*

Joints with signs of surgery (e.g. prosthesis, arthrodesis) are not scored. Also, when assessments at both time points have been done, but groups of joints are missing from one time point, the scores from that group are also set to missing at the other time point. For example if the end assessment includes only hand films (feet films missing), the initial assessment of the feet will be set to missing. Likewise, if surgery is done on a joint during the trial, the initial assessment of that joint will also be set to missing.

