15.4 Appendix D: Sharp/van der Heijde damage score

Hand radiographs are scored according to the method described by Sharp et al ([Sharp JT 1985](#)), as modified by Van der Heijde et al ([Van der Heijde DM 1989](#)). Foot radiographs are scored according to the method described by Van der Heijde et al ([Van der Heijde DM 1989](#)).

On each side of the upper limb (right and left), erosions are counted in the five metacarpophalangeal joints, the four proximal interphalangeal joints, the interphalangeal joints of the thumb, the first metacarpal bone, the radius and ulnar bones, the trapezium and trapezoid (as one unit; multangular), the navicular bone, and the lunate bone. On each side of the lower limb, erosions are counted in the five metatarsophalangeal joints and the hallux proximal interphalangeal joint.

Joint space narrowing is counted on each side of the upper limb, in the five metacarpophalangeal joints, the four proximal interphalangeal joints, the third, fourth, and fifth carpometacarpal joints, the multangulo-navicular joint, the capitato-naviculolunate joint, the radiocarpal joint. Joint space narrowing is counted on each side of the lower limb, in the five metatarsophalangeal joints and the hallux proximal interphalangeal joint.

Erosions are scored as 1 if there is a discrete interruption of the cortical surface; if there is a greater defect a score according to the surface of the joint involved is given (2-5). Consequently, for confluent erosions the score cannot become smaller. In the hands, the maximum score in a joint is 5; in the feet, it is 10.

Five grades of joint space narrowing are recognized: 0 = absent; 1 = doubtful or focal; 2 = general, less than 50% of the original joint space; 3 = general, more than 50% of the original joint space, or subluxation; 4 = ankylosis.

The maximum erosion score is 160 in the hands and 120 in the feet. The maximum joint space score is 120 and 48, respectively. The scores are added for the final radiologic score.

[figure not shown]
15.5 Appendix E:

Patient global assessment and stiffness

PATIENT GLOBAL ASSESSMENT OF DISEASE ACTIVITY

(Adapted from question 3 of the Routine Assessment of Patient Index Data (RAPID3))

Considering all the ways in which your rheumatoid arthritis has affected you, please indicate below how you have been doing the last week.

STIFFNESS

[figure not shown]

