##### *Step 2. All remaining missing damage assessments*

We may distinguish three missing data patterns in the damage scores at study onset and study endpoint:

1. Damage score is not observed at study onset but the endpoint is observed,
2. Damage score is observed at study onset but the endpoint is unobserved,
3. Damage score is neither observed at study onset nor endpoint.

The three missing data patterns are addressed as follows.

For the primary analysis, we use the algorithm 'MICE' (multiple imputation by chained equations) to impute missing measurements (van Buuren, 2012). This procedure assumes missing at random (MAR) data. The imputation models use data available at baseline (damage score at baseline, disease duration, rheumatoid factor positivity, ACPA positivity, DAS28-ESR) and the endpoint measurement of damage. Study center is not taken into account in this imputation model in view of the large number of cases with missing endpoints.

As a sensitivity analysis, we conduct a complete case analysis deleting all cases with (remaining) missing onset outcomes or missing endpoint outcomes list-wise. This analysis thus excludes cases with patterns 1, 2 and 3. This analysis assumes these outcomes are missing completely at random, MCAR (Little & Rubin, 2002).

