#### 4.10.2 Model and statistical test for the effect of treatment on damage score (hypothesis 2)

The treatment effect on the damage score at 24 months (hypothesis 2) will be evaluated by the total Sharp/van der Heijde damage score of hands and forefeet. We will use a linear mixed-effects regression model defined similarly to model 1. Contrary to model 1 there are no repeated measurements. Therefore, we model outcomes of individuals nested in centers and include as main effects treatment, design strata, and the baseline measurement of the damage score. A random effect for study center is included. Model 2 is formalized as follows:

$$\begin{aligned}
 Y_{jk} &= \delta_{0k} + \delta_{1k}S_{jk1} + \delta_{2k}S_{jk2} + \delta_{3k}T_{jk} + \delta_{4k}Z_{jk} + U_{jk} && \text{(level-1 model)} \\
 \delta_{0k} &= \gamma_{00} + V_{0k} && \text{(level-2 model for intercept)} \\
 \delta_{1k} &= \gamma_{10} && \text{(level-2 model for slope)} \\
 \delta_{2k} &= \gamma_{20} && \text{(level-2 model for slope)} \\
 \delta_{3k} &= \gamma_{30} && \text{(level-2 model for slope)} \\
 \delta_{4k} &= \gamma_{40} && \text{(level-2 model for slope)}
 \end{aligned}$$

where now  $Y_{jk}$  is the damage score at 24 months and  $Z_{jk}$  is the damage score at baseline. Equivalent to section 3.1.1, it can be see that if a one-sided t-test of  $\gamma_{30} < 0$  is significant,  $H_{0,2}$  is rejected.

We note that the damage progression measurement can be positively skewed, threatening the accuracy (type 1 error rate) of the statistical tests in small samples (and other tests of regression coefficients including t- and F-tests). If we observe a strongly skewed distribution we will apply a bootstrapped test procedure instead of the t-test.

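### When hand or foot films are missing at one visit, the SAP deletes that region at both visits without saying how the total is then formed; summing the remainder would mix scale lengths and slightly dilute the arm difference in damage

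*SAP*

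**What the plan says.** SAP 4.10.2 states that the treatment effect on damage "will be evaluated by the total Sharp/van der Heijde damage score of hands and forefeet". The model is a linear mixed model for the 24-month score; its authors "include as main effects treatment, design strata, and the baseline measurement of the damage score", with a random effect for centre.

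SAP 4.2 handles missing damage data in two steps.

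- **Step 1** concerns patients assessed at both time points. If "groups of joints are missing from one time point, the scores from that group are also set to missing at the other time point". The worked example is a whole region: "if the end assessment includes only hand films (feet films missing), the initial assessment of the feet will be set to missing". Single joints follow the same logic: "if surgery is done on a joint during the trial, the initial assessment of that joint will also be set to missing".
- **Step 2** covers what remains missing. Its three patterns are defined on the whole score, for instance "Damage score is observed at study onset but the endpoint is unobserved". Missing scores are imputed by MICE from "damage score at baseline, disease duration, rheumatoid factor positivity, ACPA positivity, DAS28-ESR" and endpoint damage. Treatment arm is not on that list. The sensitivity analysis is a complete-case analysis that drops the same three patterns.

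Protocol Appendix D gives the scale: "The maximum erosion score is 160 in the hands and 120 in the feet". For joint space narrowing the maxima are 120 and 48. It then says only that the scores are summed.

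**The concern.** After Step 1, a patient with hand films only at 24 months has no foot score at either visit. The SAP gives no rescaling, no imputation of the missing region, no minimum number of joints and no exclusion rule. By contrast, Protocol Appendix C does rescale the DAS28 and DAS44 joint terms when a joint cannot be evaluated (the 28/27 example).

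If the remaining joints are simply added, three things follow.

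- Progression in the deleted region counts as zero, so the patient contributes only part of any treatment effect.
- The baseline covariate and the imputation model mix scores of different maximum length.
- The planned complete-case analysis keeps these patients, so it would not reveal the problem.

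Damage is one of the two results that separate success, partial success and failure in benefit under SAP 4.12.

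**Working it through.** **1. Reproduce the scale in Appendix D** (two sides × sites per side × maximum grade).

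- Erosions, hands: 2 × 16 × 5 = 160. Erosions, feet: 2 × 6 × 10 = 120.
- Narrowing, hands: 2 × 15 × 4 = 120. Narrowing, feet: 2 × 6 × 4 = 48.
- Hands 160 + 120 = 280; feet 120 + 48 = 168; total 448.

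The stated maxima are reproduced exactly. Feet are 168/448 = 37.5% of the range and hands 280/448 = 62.5%.

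**2. Effect on the arm difference if the remainder is summed.** Let Δ be the full arm difference, f the share of patients with a deleted region, and w that region's share of the effect. An affected patient contributes (1 − w)Δ. With missingness unrelated to arm and a baseline slope near 1, the expected estimate is

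(1 − f)Δ + f(1 − w)Δ = Δ(1 − f·w).

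The documents give neither f nor w. Setting w to the region's share of the range is an assumption.

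| f | Feet deleted (w = 0.375) | Hands deleted (w = 0.625) |
|---|---|---|
| 5% | 1.9% lost | 3.1% lost |
| 10% | 3.8% lost | 6.3% lost |
| 20% | 7.5% lost | 12.5% lost |

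**3. Check by simulation.** The setting was 225 per arm (SAP section 6), one-sided 5% test, ANCOVA on baseline, skewed baseline and progression, no centre effect and 2000 replicates. The true difference is an assumed value, because the documents give no effect size or SD for damage. With feet deleted and w = 0.375, the full-data estimate was −0.990 and the full-data power 81.8%.

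| f | Estimate, truncated | Power, truncated | Power, prorated |
|---|---|---|---|
| 5% | −0.971 | 81.5% | 81.4% |
| 10% | −0.954 | 81.2% | 80.8% |
| 20% | −0.918 | 80.1% | 80.2% |

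Prorating brings the estimate back to about −0.99 but gains almost no power. Two harsher cases each cost 2.8 points of power: w = 0.5 at f = 20% (82.9% to 80.1%), and hands deleted at f = 10% (82.4% to 79.6%). Hands deleted at f = 20% was not simulated. Under the null with f = 20% and feet deleted, type I error was 4.8% truncated against 4.9% with full data.

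**4. Does imputing the missing region help?** This was simulated with 20% hands-only patients. Truncation retains about 92% of the effect. Imputing the foot subscore without arm in the model retains 92%, 96% and 99% when the correlation between hand and foot progression is 0, 0.5 and 0.9; the documents do not give that correlation. With arm in the model, 99-100% is retained.

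**The case against.** **The SAP does not say that the remainder is summed.** A reader might infer that truncated totals are a stated rule. They are not. If the total were instead declared missing at both visits and imputed, or rescaled, nothing would be truncated. This stands, and it makes part of the point a gap in the text. Summing is still the most natural reading, because matched deletion serves no purpose if the total is then discarded. The deletion itself is explicit.

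**Matched deletion has a good purpose.** Without it, a hands-only end score set against a hands-and-feet baseline would show a false fall of up to the whole baseline foot score. This stands, and the rule suits single joints. One foot joint carries at most 10 + 4 = 14 of 448 points (3.1%).

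**A reader might call the rule perverse**, since a patient with no end films receives a full-scale imputed total while one with good hand films receives a shortened one. The documents do not support that for the treatment effect. Arm is not among the listed imputation variables, so on that list a wholly imputed endpoint carries little or none of the arm difference. The hands-only patient keeps the real difference in the hands.

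**A reader might infer a material threat to the benefit verdict.** Nothing supports a high share of partial film sets. Protocol 9.3.3 schedules hands and forefeet together, and the SAP's remark that many endpoints are missing does not count partial sets. At 5-10% lacking feet, the simulated power loss is under 1 point. The bias also runs toward the null, so it does not favour a false claim of benefit.

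**Conclusion.** The point holds in a limited form and is minor. Step 1 deletes a whole observed region, Step 2 does not restore it, and the scoring of the remainder is undefined. On the natural reading, the cost is mainly a diluted estimate and a covariate of mixed scale. With feet deleted, dilution is about 2-4% when 5-10% of patients are affected and 7.5% at 20%. With hands deleted in 20%, it reaches 12.5%.

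These figures assume that missingness is unrelated to arm, that the deleted region's effect has the same direction, and that its share of the effect equals its share of the range. The actual number of partial film sets could make the issue negligible. It should be counted before anyone draws a stronger conclusion.

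**What to change.** - Keep matched deletion for single operated or unreadable joints.
- When a whole region is missing at one visit, keep the observed hand and foot subscores. Put the hand and foot subscores at both visits **and treatment arm** into the planned MICE model, impute the missing subscore, and sum to the 0-448 total. The subscores alone are not enough when hand and foot progression are weakly correlated.
- Report the number of patients with a deleted region, by arm and by region.
- As sensitivity analyses, keep the available-region score, with its scoring rule written out, and add an analysis limited to complete hand-and-foot pairs.

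The cost is SAP wording and a few more variables in an imputation that is already planned; no new data are needed. The downside is slightly more imputed data and a slightly larger standard error.

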##### *Step 2. All remaining missing damage assessments*

We may distinguish three missing data patterns in the damage scores at study onset and study endpoint:

1. Damage score is not observed at study onset but the endpoint is observed,
2. Damage score is observed at study onset but the endpoint is unobserved,
3. Damage score is neither observed at study onset nor endpoint.

The three missing data patterns are addressed as follows.

For the primary analysis, we use the algorithm 'MICE' (multiple imputation by chained equations) to impute missing measurements (van Buuren, 2012). This procedure assumes missing at random (MAR) data. The imputation models use data available at baseline (damage score at baseline, disease duration, rheumatoid factor positivity, ACPA positivity, DAS28-ESR) and the endpoint measurement of damage. Study center is not taken into account in this imputation model in view of the large number of cases with missing endpoints.

As a sensitivity analysis, we conduct a complete case analysis deleting all cases with (remaining) missing onset outcomes or missing endpoint outcomes list-wise. This analysis thus excludes cases with patterns 1, 2 and 3. This analysis assumes these outcomes are missing completely at random, MCAR (Little & Rubin, 2002).

#### *Handling of missing harm outcomes*

Harm is verified throughout the trial via remote and onsite checks against the source data. So harm assessment is assumed to be complete.

### **4.3 Baseline definition**

Baseline is defined as the last value immediately before the start of the treatment.

## **4.4 Definition of study visit and visit window**

### **4.4.1 Study visit**

The baseline visit (visit 1, in the clinic) is defined as study month 0. The next visits are at 3 months (visit 2, in clinic), 6 months (visit 3, in clinic), 9 months (visit 4, remote), 12 months (visit 5, in clinic), 15 months (visit 6, remote), 18 months (visit 7, in clinic), 21 months (visit 8, remote), 24 months (visit 9, in clinic), 27 months (10, in clinic). The end of the study is defined as the date of the last study visit.

### **4.4.2 Visit window**

The protocol allowed to minimize or maximize the visit window with two months. For the radiology data (x-rays hand and forefeet and DEXA), the time window for the baseline measurement was 6 months before or 3 months after the baseline visit, and for the 24-months measurement 3 months before or after visit 9. If these are exceeded we will accept images up to 1 year before and 6 months after baseline, and up to 1 years after year 2. Data will be analyzed based on the visit number/month that is reported in the database. The calendar visit dates will not be used.

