9.3.3 Hand, wrist and feet X-ray

Radiographs of both hands (including wrists) (one film anteroposterior) and forefeet (one film anteroposterior) will be obtained at baseline and 24 months.

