9.6 Follow-up of subjects withdrawn from treatment

All patients taking study medication will be followed up for a maximum of 2 years and 3 months, when tapering of study medication is complete. When a patient prematurely discontinues study medication a full end of study visit (V9) is performed. This visit includes radiographic assessment (X-ray and DEXA) if study medication is stopped at or after 9 months from study start and if local standards permits.

Where this is not possible (because the stop of study medication lies in the past), the first visit after the event must be executed as a V9 visit.

For completeness: regulations stipulate that all adverse events (serious or nonserious) MUST be followed until resolved or stable, this also applies to situations where study medication is prematurely stopped. For all adverse events the last possible follow up will be at V10.

In addition, all patients stopping prematurely are invited to attend a follow up visit (V10) at or around 2 years after the inclusion date. Data collected at this visit is the same as those collected for a normal V10 ('follow up/taper visit').

For patients who stop prematurely, AE evaluation will be limited to SAE and events of special interest. At visit 10, completeness of follow up for events occurring in the first 3 months after stop of study medication will also be checked.

Completion of the data for V10 is required to receive the full fee for a patient.

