**Figure 1: Schedule of assessments**

	Base-line	2 year treatment period									Follow-up / taper
		1	2	3	4	5	6	7	8	9	
Visit No	1										10
Month (visit window +/- 2 months)	0	3	6	9	12	15	18	21	24 lv	27	
Location	clinic	clinic	clinic	remote	clinic	remote	clinic	remote	clinic	clinic	
Written informed consent	X										
In- / exclusion criteria	X										
Demographics, education & medical history	X										
Baseline prognostic factors: adherence, health literacy, arthritis helplessness index	X*										
Randomization	X*										
Physical examination	X										
Height	X									X	
Vital signs / weight	X	X	X		X		X		X	X	
AE evaluation (inc. surgery, comorbidity) (safety)		X*	X*	X*	X*	X*	X*	X*	X*	X*	
Concomitant medication	X	X	X	X	X	X	X	X	X	X	
Lab (hematology  , chemistry  )	X	X	X		X		X			X	
Lab lipids 	X	X			X 					X	
Lab CRP, ESR	X	X	X		X		X		X	X	
Joint counts (44) (effectiveness)	X									X	
Joint counts (28) (effectiveness)		X	X		X		X			X	
DEXA either with VFA, or without VFA plus X-lat spine (thor, lumb) 	X									X	
X-rays hand and forefeet  (safety)	X									X	
Patient global assessment, stiffness duration, stiffness severity	X	X	X	X	X	X	X	X	X	X	
Physician global assessment	X	X	X		X		X		X	X	
Questionnaires:											
- RAID	X*	X*	X*	X*	X*	X*	X*	X*	X*	X*	
- full HAQ-DI (24 items)	X*	X*	X*		X*		X*		X*	X*	
- MHAQ-DI (10 items)				X		X		X			
- Cost questionnaire	X*	X*	X*		X*		X*		X*	X*	
- EQ-5D	X*	X*	X*	X*	X*	X*	X*	X*	X*	X*	
- SF36	X*								X*	X*	
- Patient symptom list	X*								X*	X*	
GC or placebo, dispense adherence	X*	X*	X*	X*	X*	X*	X*	X*	X*	X*	

\* procedures not belonging to standard of care

lv End of study visit. This visit also needs to be completed by subjects who early terminated the trial.

Apart from CRP and ESR, the following standard of care lab tests will be done on peripheral blood samples.

Lab results of CRP and ESR no more than 4 weeks old may be used for the baseline visit.

Results of the below tests  no more than 2 months old may be used for the baseline visit:

1) Hemoglobin, Mean Cell Volume, White blood cell count, White blood cell differential count, Platelet count.

2) Glucose (non-fasting), Creatinine, Alanine Aminotransferase;

3) Total cholesterol, HDL cholesterol. Optional for month 12.

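### The SAP does not fix which month an early-termination V9 represents; read literally, its visit rule turns early films, DEXA and DAS28 into 24-month values, against other text in the plan

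*SAP*

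**What the plan says.** Text that makes an early-stop visit a month-24 visit:

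- Protocol 9.6: "When a patient prematurely discontinues study medication a full end of study visit (V9) is performed". If the stop is discovered late, the next visit is run as V9. On imaging: "This visit includes radiographic assessment (X-ray and DEXA) if study medication is stopped at or after 9 months from study start", where local standards allow.
- SAP Figure 1, footnote to the month-24 column: "This visit also needs to be completed by subjects who early terminated the trial".
- SAP 4.4.1 sets visit 9 at month 24 and visit 10 at month 27.
- SAP 4.4.2: "Data will be analyzed based on the visit number/month that is reported in the database. The calendar visit dates will not be used".

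Text that points the other way or leaves the matter open:

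- Protocol 9.3.3 plans hand films and "forefeet (one film anteroposterior) will be obtained at baseline and 24 months".
- SAP 4.4.2 gives the end-imaging window as "for the 24-months measurement 3 months before or after visit 9". The relaxed limit runs "up to 1 years after year 2", with no matching extension before it.
- SAP 4.2 classes DAS28 after premature discontinuation as monotone missing, and the nonresponder check codes incomplete units as 0. A damage score present at onset but not at the endpoint is a missing-endpoint pattern, filled by MICE.
- Protocol 11.1 lets a discontinuation visit contribute up to the stop, without giving it a month.
- Protocol 9.6 also invites early stoppers to a V10 about two years after inclusion.

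**The concern.** The two groups of statements give different 24-month datasets. Under the literal rule, a film taken at month 12 because the patient stopped is the 24-month damage score, and a DAS28 taken at month 5 is the month-24 DAS28. Under the other statements both are missing at month 24.

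Damage is one of the two benefit outcomes in the success rule (SAP 4.12), and model 2 uses a single end score with no term for the interval. Bone mass is among the few secondary outcomes formally tested for harm (SAP 4.13). The nonresponder check depends directly on who counts as complete at the end. The complete-case sensitivity analysis for damage would not reveal the problem, because a labelled early film looks complete.

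**Working it through.** The plan states no figure that depends on this label, so there is nothing to reproduce. The check is a comparison of texts, followed by illustrations under stated assumptions.

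**1. Texts side by side.**
- *Film at month 12.* If visit 9 in the window means month 24, the film is 24 − 12 = 12 months early and outside the 3-month limit. If it means the visit actually held, the film is 0 months away and inside.
- *DAS28, stop at month 5.* By label, the patient has values at months 3 and 24 and none at 6, 12 and 18. That gap is not monotone, so SAP 4.2's description of discontinuation does not fit this patient. Model 1 has five fixed post-baseline occasions and no slot for an off-schedule visit.
- *Two-year value.* The same patient's real two-year assessment is a V10, which the rule labels month 27, outside the 24-month analysis.

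**2. Interval covered by an early film, linear change assumed.** Fraction = t/24: month 9, 9/24 = 37.5%; month 12, 50%; month 15, 62.5%; month 18, 75%.

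**3. Unequal numbers of early films.** Spurious difference = common 24-month progression × (1 − m/24) × difference in share. At mean film month m = 15 and a 10-point difference:

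| Progression (assumed) | Calculation | Units |
|---|---|---|
| 1 | 1 × 0.375 × 0.10 | 0.0375 |
| 3 | 3 × 0.375 × 0.10 | 0.1125 |
| 5 | 5 × 0.375 × 0.10 | 0.1875 |

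The error runs against the arm with fewer early films.

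**4. Equal numbers of early films.** If the drug effect is taken to continue after stopping, the contrast shrinks by share × (1 − m/24). At m = 15, shares of 5% to 35% give 0.05 × 0.375 = 1.9% to 0.35 × 0.375 = 13.1% (m = 12: 2.5% to 17.5%; m = 18: 1.3% to 8.8%).

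**5. Treatment-policy target.** Suppose instead that both arms progress equally after stopping. A stopper's contrast at month 24 is then the D × m/24 already accrued. The overall contrast is (1 − s)D + sD × m/24 = D(1 − s(1 − m/24)), which is exactly what the label gives when stopping is equal.

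**6. Imputation.** SAP 4.2 lists the damage predictors as baseline damage, disease duration, rheumatoid factor, ACPA, DAS28-ESR and endpoint damage. Treatment is not listed. Imputed endpoints then carry almost no treatment contrast, so the overall contrast is roughly (1 − share imputed) × D. A simulation agrees (450 patients, 1,500 runs; assumed progression 3 on placebo and 1.5 on prednisolone, SD 5; early films uniform over months 9 to 21; 20 imputations). At a 25% share:

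| Handling | Effect | Shrinkage |
|---|---|---|
| Full data (effect continues) | −1.495 | – |
| By label | −1.355 | 9.4% |
| Imputed without treatment | −1.114 | 25.5% |
| Imputed with treatment | −1.486 | 0.6% |

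**7. Nonresponder check.** For each 10% of patients who stop early with a V9, of whom an assumed 20% to 40% have a DAS28 change below −0.6, 0.10 × 0.20 = 2 to 0.10 × 0.40 = 4 points per arm move to responder if the label overrides SAP 4.2.

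**8. Time-averaged DAS28.** Simulated with an assumed effect of −0.40 and a flare of 0.6 at stopping; early V9 labelled month 24 versus dropped:

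| Stopping, prednisolone / placebo | Labelled | Dropped |
|---|---|---|
| 30% / 30% | −0.40 | −0.40 |
| 30% / 45% | −0.42 | −0.39 |
| 21% / 51% | −0.46 | −0.41 |

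The gap is 0.00 to about 0.05.

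**The case against.** The strongest reply is that the plan can be read sensibly as it stands. SAP 4.4.2 sets aside calendar visit dates, not image dates, and its windows cannot be applied without image dates. With visit 9 at month 24, films before month 21 fall outside the window and become missing endpoints. SAP 4.2 likewise makes early stoppers nonresponders. The database may code early terminations separately, and a rule in appendix pages not available here cannot be excluded. All of this stands as a reasonable reading, but no available text selects it over the literal one.

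A reader might also infer that labelling biases the damage contrast, or hides bone harm, by 2% to 13%. The documents do not support that. The figure assumes that the drug effect continues after stopping, whereas SAP section 2 describes the effect of a treatment policy irrespective of adherence. Step 5 shows a plausible case with no bias against that target. At 25% early films and mean month 15, imputation with treatment would there exceed the policy contrast by about 10% (1/0.906). The unequal-stopping term remains.

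Nor is the main DAS28 result in doubt: the harm co-primary is untouched, and the time-averaged estimate barely moves.

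**Conclusion.** The point holds as a conflict in the plan. Protocol 9.6, the Figure 1 footnote, SAP 4.4.1 and SAP 4.4.2 together make an early V9 a 24-month value, while SAP 4.2 and the one-sided relaxation of the imaging window imply that it is not. The database label is not shown, so competing 24-month datasets are possible.

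The size is unknown. Early films need a stop at or after month 9 and local permission, and no share is given. The supportable illustration is 0.04 to 0.19 damage units per 10-point difference between arms, assuming linear change, mean film month 15 and 1 to 5 units of common progression. The omission of treatment from the listed imputation predictors is a separate weakness and potentially the larger one, with dilution of about 25% at a 25% imputed share against a continuing effect. The conflict should be settled before the blind is broken, but it does not threaten the time-averaged DAS28 conclusion.

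**What to change.** 1. In SAP 4.4.2, define the end-imaging window as 3 months either side of month 24 from randomisation, by image date, and keep the existing relaxation after year 2. Hand and foot films outside it are the missing-endpoint pattern of SAP 4.2; DEXA outside it is missing at month 24.
2. In SAP 4.2, add treatment arm to the damage imputation model, and run one sensitivity analysis that uses early films over their actual interval. Items 1 and 2 belong together: without treatment in the model, setting early films to missing dilutes the contrast more than the literal label does (about 25% against 9% in the example).
3. In SAP 4.4.2, state that an early-termination V9 DAS28 counts as month 24 only within the existing 2-month window around it. Otherwise it goes to the nearest unfilled scheduled occasion by date.
4. In the nonresponder check, state that an early V9 outside that window does not make a unit complete.
5. State how a V10 held at about two years in an early stopper is labelled, consistently with the treatment-policy principle in SAP section 2. Reconcile Protocol 9.6 and 11.1 with SAP 4.2 and 4.4.2.

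The cost is a few SAP sentences, one imputation covariate and a little programming; image dates are already needed for the stated windows. The downside is that more damage endpoints rest on the missing-at-random assumption, in a trial where SAP 4.2 already expects many to be missing. Such imputation also leans towards an effect that continues after stopping, so the report should say which effect the damage analysis estimates.
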